Objective 1: To evaluate the comparative effectiveness of patient-centered messages to enhance clinical trial participation, through a culturally tailored website, accessed using iPads, versus NYU's standard clinical trial participation website.

Hypothesis 1: Participants exposed to tailored messages about clinical trial literacy will exhibit greater likelihood in participating in clinical trials than those exposed to NYU's standard website.

Objective 2: To determine whether psychosocial factors (awareness of clinical trial, intrinsic motivation, health literacy, and self-efficacy) and medical factors (risk behavior, history of preventive behavior, and clinical diagnoses) mediate greater likelihood of participating in clinical trials among individuals exposed to the intervention.

[figure not shown]
Hypothesis 2: Greater likelihood of participating in clinical trials will be mediated by greater health literacy and self-efficacy independent of other individual-level factors (medical, knowledge, attitude/beliefs, and intrinsic motivation) and contextual-level factors (social support and socio-economic position).

Study Design

Objective 1: To evaluate the comparative effectiveness of a culturally and linguistically tailored clinical trial literacy website in increasing likelihood of participating in clinical trials. To achieve this objective, we will use a randomized group design, assessing the following patient-centered outcomes: willingness to enroll in clinical trials and behavioral intent as well as likelihood of referring others to enroll in such trials) before and after exposure to a culturally-tailored clinical trial literacy website. Health literacy will be measured both before and post exposure to tailored messages.

Participants will be randomized into two groups. The intervention group (n=50) will have access to culturally tailored website. Participants in the control group (n=50) will have access to NYU 's standard trial participation website.

Study Flowchart

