Medical Outcomes Study Short Form 36	X		
Internet Self-efficacy Scale	X	X	X
Clinical Trials Literacy	X	X	X

Message Effectiveness Scale		X	X
Clinical Vignette			X

IV. DATA ANALYSIS AND DATA MONITORING

Throughout the study, [name] will oversee data entry and verification, ensure adherence to coding, clean and edit protocols. Data will be maintained on a password-protected PC with backup copies kept on external disks in a secured location.

Participant-identifying information will be kept in a locked file cabinet with only numerical identifiers in computer files.

Hypothesis 1: Participants exposed to tailored messages about clinical trial literacy will exhibit greater likelihood in participating in clinical trials than those exposed to NYU's standard website. Secondly, we expect them to show greater likelihood to refer others to clinical trials as well.

Analysis: While the primary goal of the study is to develop and test effectiveness of tailored messages to overcome identified barriers to participating in clinical trials, the secondary goal is to examine factors likely to facilitate adoption of such messages. All participants in the intervention arm will have been exposed to all tailored web-based messages. To compare participants who exhibited improvement in health literacy and those who did not 2-months post-enrollment, t-tests and chi-squared tests will be used. Baseline subjective factors will be entered in a logistic regression model in order to determine which factors are associated with higher likelihood of (a) registering to participate in clinical trials, contrasting individuals in the two study arms and (b) referring others to participate as well. Multivariate analysis of covariance will be used to assess effects of messages on the secondary outcome: health literacy scores; effects of sociodemographic confounders will be adjusted.

Hypothesis 2: Greater likelihood of participating in clinical trials will be mediated by greater health literacy and/or self-efficacy independent of other individual-level factors (medical, knowledge, attitude/beliefs, and intrinsic motivation) and contextual-level factors (social support and socio-economic position).

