Analysis: We will examine the path toward greater participation in clinical trials using Structural Equation Modeling (SEM). SEM will determine influences of mediating/moderating factors on the role of tailored messages in improving participation rates in existing clinical trials. Specifically, we will use moderated path analysis from Baron and Kenny's model. We chose these factors based on research showing acceptable effect size in predicting likelihood of increased participation. Alternatively, we will employ probabilistic modeling methods (e.g., Bayesian Belief Network) to investigate interactions (omni-directionality) among predictors and different pathways to the desired study outcomes, determining which factors best differentiate cases and controls. Thus, we will ascertain patient characteristics most likely to show improvement in rates of participation.

V. STATISTICAL PLAN

Power Calculations: Primary Objective: Assuming a medium effect size ($d = 0.32$), as derived from Cohen, and a sample size of 100, the study will be adequately powered (> 80%) to detect significant differences between participants likely to show improvement in health literacy scores and those who are not using Fisher's Exact tests (critical $X^2 = 6.58$). This will also permit detection of a significant increase in the number of participants in the intervention arm opting to register for clinical trials. In a previous pilot study, we found that 45% of minority patients in the community adopted recommendations for medical treatments after exposure to tailored health messages, which compares to 25% who did without such exposure. Assuming a 20% increase in the likelihood of adopting health messages and a sample size of 100, the proposed study will have adequate power for a preliminary test of the hypothesis that exposure to health messages will foster greater uptake of tailored health messages and improvement in clinical trial health literacy level. Achieving the goal of a 20% increase would have an important public health impact regarding adoption of messages about clinical trials. A two-tailed test, with 80% power and $\alpha = 0.05$ comparing 25% to 45% requires 50 participants per arm. The study is powered to assess differences in participation rates between the two arms as well as the mediating effect of individual and contextual factors between tailored clinical trial messages and participation rates, considering a 23% attrition rate.

VI. DATA HANDLING

Confidentiality

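### Hypothesis 2 cites Baron and Kenny but specifies no estimate, interval or test of the indirect effect; if the classical steps are meant, power for mediation is capped by total-effect power

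*Combined protocol and SAP*

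**What the plan says.** Objective 2 is one of the plan's two objectives, and its hypothesis is a mediation claim. In the objectives it reads "Greater likelihood of participating in clinical trials will be mediated by greater health literacy and self-efficacy". In section IV the wording is "will be mediated by greater health literacy and/or self-efficacy independent of other individual-level factors", so it is not settled whether both mediators are needed or either will do.

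The section IV analysis paragraph for Hypothesis 2 opens with structural equation modelling (SEM), speaks of mediating and moderating factors together, and then narrows: "we will use moderated path analysis from Baron and Kenny". A Bayesian Belief Network is offered as an alternative, to explore interactions and pathways. The paragraph gives no estimate, confidence interval or test of an indirect effect, and does not say whether a significant total effect must come first.

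Section V gives one full sample-size calculation, for two proportions: "comparing 25% to 45% requires 50 participants per arm". It then says that the study is also powered for the mediating effect, allowing for 23% attrition. It shows no path values and no calculation for that claim.

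**The concern.** In its classical form the Baron and Kenny procedure asks for a significant total effect of arm on outcome, a significant effect of arm on mediator (path a), a significant effect of mediator on outcome given arm (path b), and a direct effect smaller than the total. Mediation is inferred from that pattern. The product a × b, which is the mediated effect, is neither tested nor reported with an interval.

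Two things are at stake. If the total-effect condition is applied, the analysis can conclude that there is no mediation merely because the arm comparison missed significance, and this trial has limited power for that comparison. And even a positive result would not say how much of the effect runs through literacy or self-efficacy, which is what Objective 2 sets out to learn.

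**Working it through.** **Inputs from the plan.** 25% against 45%, two-sided α = 0.05, 80% power, 50 per arm, total 100, attrition 23% (100 × 0.77 = 77, or 38.5 per arm), and d = 0.32 (section V; the arm sizes are also in the Study Design section). The 25% and 45% are pilot rates for adopting treatment recommendations, used by the plan as its working rates.

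**The plan's own figure.** With pooled variance under the null, n per arm = [1.96√(2 × 0.35 × 0.65) + 0.8416√(0.25 × 0.75 + 0.45 × 0.55)]² / 0.20² = (1.322 + 0.555)² / 0.04 = 88.1, so 89. The stated 50 does not reproduce. With attrition, 89 / 0.77 = 115.6, so 116 per arm. That is a separate and larger problem; here it matters because it fixes total-effect power.

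**Total-effect power.** Power = Φ{[0.20 − 1.96√(0.455/n)] / √(0.435/n)}.
- n = 50: (0.20 − 0.1870) / 0.0933 = 0.14, giving 56% (Fisher's exact test 48%).
- n = 38.5: (0.20 − 0.2131) / 0.1063 = −0.12, giving 45% (Fisher 36% at 38 per arm).

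A procedure that requires this test to be significant cannot have more power than the test, however strong the mediator.

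**Size of the loss.** The documents give no arm-to-mediator effect, b path or direct effect, so every row below is an assumption. Using 0.32 as a mediator shift is also an assumption, since section V attaches it to a different comparison. Entries are simulated power for the classical steps, then for an interval for a × b. The binary rows use a percentile bootstrap, fix the outcome at 25% against 45%, and use linear probability models without the check that the direct effect is smaller than the total. The continuous rows use a percentile bootstrap or a Monte Carlo interval; where a range is shown, it spans repeated simulations.

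| Outcome and assumed paths | N = 100 | N = 77 |
|---|---|---|
| Binary, shift 0.32 SD, 25% mediated | 19% vs 31% | 16% vs 26% |
| Binary, 0.32 SD, 50% mediated | 29% vs 37% | 24% vs 32% |
| Binary, 0.5 SD, 25% mediated | 23% vs 37% | 13% vs 25% |
| Binary, 0.5 SD, 50% mediated | 46% vs 71% | 32% vs 59% |
| Binary, 0.5 SD, 80% mediated | 50% vs 73% | 39% vs 61% |
| Binary, 0.8 SD, 100% mediated | 54% vs 98% | 47% vs 94% |
| Continuous, 0.32 SD, b = 0.4, direct 0.22 | 17% vs 35% | 11% vs 25% |
| Continuous, 0.5 SD, b = 0.4, direct 0.22 | 37–43% vs 68–70% | 25–31% vs 53–56% |
| Continuous, 0.5 SD, b = 0.4, no direct effect | 13–15% vs 68–69% | 9–10% vs 53–55% |
| Continuous, 0.78 SD, b = 0.39, no direct effect | 27% vs 93% | 20% vs 81% |
| Continuous, 0.78 SD, b = 0.39, direct 0.78 | 93% vs 93% | 83% vs 83% |

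The no-direct-effect rows with a 0.5 SD shift imply a total effect of only 0.5 × 0.4 = 0.20 SD. They are therefore not the same scenario as 25% against 45%.

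**False positives.** With no mediation (a = 0), the percentile bootstrap rejected in about 3% to 6% of runs at these sample sizes. The bias-corrected bootstrap rejected in about 7% to 8%.

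**Where the gain comes from.** Requiring only a and b to be significant gives nearly the same power as the bootstrap (69% vs 71% at N = 100 and 57% vs 59% at N = 77 for the 0.5 SD, half-mediated binary case). The power comes from dropping the total-effect condition; what the interval adds is the size of the mediated effect.

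**The case against.** The strongest reply is that the plan never writes out the causal steps. It names SEM and path analysis, both of which yield a and b and hence a × b, and a reference to Baron and Kenny's model could mean only the mediator path diagram. That stands. A reader might infer that the plan commits itself to a total-effect gate and so will miss mediation; the text does not say so, and the power figures apply only if the classical steps are used. The plan still supplies no other rule, and the sentence that narrows the SEM approach points to Baron and Kenny. Either reading therefore needs the same clarification. The Bayesian network is described as exploratory and does not supply the missing test.

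A second reply is that the size of the loss is a matter of assumption. That also stands: with a large direct effect there is none. The loss is greatest when the website acts mainly through literacy or self-efficacy, which is close to what Hypothesis 2 proposes.

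A third is that this is the second objective of a pilot, and that the sample size is the main weakness. Both are true. They bear on priority, not on whether the sentence should be corrected.

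**Conclusion.** The concern holds as a gap in specification with a conditional cost. The plan names Baron and Kenny within SEM and gives no estimate, interval or test of the indirect effect. If the classical steps are followed, power for mediation is at most about 56% at N = 100 and 45% at N = 77 on the plan's own rates, and no size of mediation is reported. Against an interval for a × b, the loss is nil with a large direct effect; about 8 to 18 points with a 0.32 SD mediator shift and partial mediation; about 25 to 31 points with a 0.5 SD shift about half mediated; and about 43 to 65 points with full mediation, a shift of 0.5 SD or more and b near 0.4 or above. All of these rest on assumed paths.

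Two stronger readings are not supported. The loss is not large in every scenario. Nor does the bootstrap make the trial adequately powered: at a 0.32 SD shift with partial mediation its power is about 25% to 37%, and with a 0.5 SD shift half mediated it is 59% to 71%. The statement in section V that the study is powered for the mediating effect has no calculation behind it.

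**What to change.** In section IV, Hypothesis 2, replace the Baron and Kenny sentence with:

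> The indirect effect (a × b) of arm through clinical trials literacy and through self-efficacy will be estimated in the SEM/path model with percentile bootstrap 95% confidence intervals (at least 5000 resamples). A significant total effect is not required. For binary registration, indirect effects are reported on the probability scale. Any moderation analysis is separate.

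Use the percentile interval and not the bias-corrected one, whose type I error is inflated at this sample size. State the time points at which mediator and outcome are taken, and settle whether the hypothesis concerns both mediators or either.

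In section V, remove the statement that the study is powered for the mediating effect, or label Objective 2 exploratory.

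The cost is a few sentences of analysis plan and standard software. Table 1 already has clinical trials literacy and internet self-efficacy at baseline, 1 month and 3 months, so no participants, visits or measures are added. This is a free improvement, but it does not cure the sample size.

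### The first power sentence in Section V combines an effect size, a test and a critical value that do not fit together, so its claim of more than 80% power is not supported as written

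*Combined protocol and SAP*

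**What the plan says.** Section V (Statistical Plan, Power Calculations) gives two calculations in one paragraph.

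- **First calculation, labelled as the primary objective.** It starts from "Assuming a medium effect size ($d = 0.32$), as derived from Cohen, and a sample size of 100" and concludes that "the study will be adequately powered (> 80%) to detect significant differences". The groups are "participants likely to show improvement in health literacy scores and those who are not", and the method is given as "using Fisher's Exact tests (critical $X^2 = 6.58". Degrees of freedom, group sizes and alpha are not given. The next sentence says the same calculation also covers an increase in registration for trials in the intervention arm.
- **Second calculation.** "A two-tailed test, with 80% power and $\alpha = 0.05$ comparing 25% to 45% requires 50 participants per arm". This is the only place in the section where alpha is stated. The paragraph ends by saying that 23% attrition has been considered.

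In Section IV (Hypothesis 1, Analysis), the comparison of participants whose health literacy improved with those whose did not is assigned differently: "t-tests and chi-squared tests will be used". Fisher's exact test is not named there. Registration and referral are to be analysed by logistic regression.

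**The concern.** The symbol d normally denotes a standardised difference between two means, which does not belong with a test on a two-by-two table. Fisher's exact test takes its p-value from the hypergeometric distribution and uses no chi-squared cut-off. The cut-off quoted is also not the 5% value on 1 df. A reader therefore cannot tell which effect, test and significance level produced the figure of more than 80%.

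This is the power statement attached to the primary objective, and it looks like an independent justification for N = 100. If only the later 25% versus 45% sentence were corrected, this one would remain as apparent support for the sample size. The sentence also extends its conclusion to registration by arm, which is a different comparison with a different stated effect.

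**Working it through.** **Inputs.** From Section V: effect 0.32, N = 100, power above 80%, critical value 6.58, rates 25% and 45%, attrition 23% (100 × 0.77 = 77 completers). From the Study Design: 50 per arm. Assumptions: two-sided alpha 0.05, carried over from the second calculation to the first, and equal groups of 50, because the sizes of the improver and non-improver groups are not given.

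**Step 1: 0.32 as a standardised mean difference.**
Power ≈ Φ(d√(n/2) − 1.96) = Φ(0.32 × 5 − 1.96) = Φ(−0.36) = 36%; the noncentral t gives 35%.
For 80% power, n = 2(1.96 + 0.8416)²/0.32² = 15.70/0.1024 = 153.3, so about 154 per group.
An unequal split lowers power further: 33% at 35/65 and 28% at 25/75.

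**Step 2: the critical value.**
The 0.05 chi-squared values are 3.84, 5.99 and 7.81 on 1, 2 and 3 df. The tail probability beyond 6.58 is 0.010, 0.037 and 0.087 respectively, so 6.58 matches 0.05 on none of them.
Keeping 6.58 (√6.58 = 2.565) with d = 0.32 gives Φ(1.6 − 2.565) = 17%.

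**Step 3: 0.32 as Cohen's w on 1 df.**
Noncentrality λ = N·w². Power ≈ Φ(√λ − √critical value).

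| N | λ | √λ | Power at 3.84 | Power at 6.58 |
|---|---|---|---|---|
| 100 | 10.24 | 3.200 | 89% | 74% |
| 77 | 7.88 | 2.808 | 80% | 60% |

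The plan's figure is reproduced in the 3.84 column. N = 77 is also the smallest total that reaches 80% (80.2%; N = 76 gives 79.7%), and it is what 23% attrition leaves from 100.

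**Step 4: is 0.32 the planned contrast between arms?**
For 25% versus 45%, the mean rate is 0.35, so w = 0.20/(2√(0.35 × 0.65)) = 0.20/0.954 = 0.21. Cohen's h = 2·arcsin√0.45 − 2·arcsin√0.25 = 1.471 − 1.047 = 0.42. Neither is 0.32. With 25% in controls, w = 0.32 would need about 56% in the intervention arm.

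**Step 5: power for 25% versus 45%, two-sided 0.05.**
At 50 per arm, the standard error is √(2 × 0.35 × 0.65/50) = 0.0954 under the null and √((0.1875 + 0.2475)/50) = 0.0933 under the alternative. Power = Φ((0.20 − 1.96 × 0.0954)/0.0933) = Φ(0.14) = 56%.
Enumerating all tables gives 56% for Pearson's chi-squared and 48% for Fisher's exact test at 50 per arm. With 77 completers (38 control, 39 intervention) it gives 46% and 39%.

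**The case against.** The best defence is that this is a notation slip. If 0.32 is w, tested on 1 df at 0.05, power is 89% at N = 100 and just reaches 80% at exactly the number left after the stated attrition. That match is unlikely to be chance and suggests a sound calculation written down with the wrong symbol and the wrong cut-off. This part of the objection stands. A reader might infer that power is below 80% on every reading, or that the trial's true power is 35%. The documents support neither: the 35% depends on taking the letter d literally for a test described on a two-by-two table, and on assumed group sizes and alpha.

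Three further points have some force.

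- Alpha 0.05 is stated only for the second calculation. If 6.58 was deliberate, however, power on 1 df is 17% (d) or 74% (w), still short of the claim.
- Different endpoints may have different effect sizes, so 0.32 and 25% versus 45% need not agree. The difficulty is narrower: the text says the first calculation also covers registration by arm.
- Fisher versus chi-squared matters little at this effect. With w = 0.32 and 50 per arm, Fisher gives about 87–88% against 89%.

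Other readings also exceed 80%, but they do not fit the text. A paired or one-sample d with n = 100 gives 89%, yet two groups are described. Keeping 6.58 on 3 df with w = 0.32 gives 84%, but at alpha 0.087 and with no basis in a two-by-two comparison.

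The pilot label and the description of the test as preliminary make modest power acceptable. They do not make an unsupported figure correct.

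**Conclusion.** Wrong as written. The figure of more than 80% does not follow from d = 0.32, Fisher's exact test and a critical value of 6.58 taken together. Literally, d = 0.32 gives about 35% (two-sided 0.05, 50 per group). On 1 df, the stated figure is recovered by changing two of the printed elements, the effect-size label and the cut-off; correcting the label to w and keeping 6.58 leaves 74% at N = 100 and 60% at N = 77. A mislabelled w is the likeliest explanation, but the documents do not confirm it.

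Even so corrected, the sentence would not support the trial's comparison of arms. As worded it contrasts improvers with non-improvers, and w = 0.32 is larger than the w = 0.21 implied by 25% versus 45%. For that contrast, power is about 56% at 50 per arm and 46% at 77 completers (chi-squared), assuming the stated rates and attrition spread about evenly over the arms. The statement that "comparing 25% to 45% requires 50 participants per arm" is a related but separate error, and correcting it would not repair this sentence.

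**What to change.** In Section V:

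- Delete the critical value of 6.58 and correct the effect-size label.
- For the health-literacy comparison, state the metric, the groups and their expected sizes, a test that matches Section IV, the degrees of freedom, alpha, and the power recalculated from these, with and without 23% attrition.
- Remove the statement that this calculation also covers registration by arm. Give that comparison its own sentence: 25% versus 45%, two-sided 0.05 (chi-squared critical value 3.84), power about 56% by chi-squared at 50 per arm and about 46% at 77 completers. If Fisher's exact test is intended, the figures are 48% and 39%, and Section IV should name it.
- Since Section IV assigns registration to logistic regression, say that the two-proportion figure is an unadjusted approximation, or align the two sections.

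The cost is wording only, with no change to design or data collection. The stated power becomes less favourable.

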Participants randomized to the control condition will have free access to the NYU standard clinical trials website. Currently, there is no specific comparative effectiveness data evidencing superiority of any website or other format for increasing clinical trials literacy. Furthermore, there has been previous research to suggest the overall difficulty that patients have in using generic, versus tailored clinical trial materials. This, our study will ascertain effectiveness of a tailored website compared to the standard website. Participants in the control condition will have access to the tailored website at the date of study completion (no later than 6 months' post-date of enrollment).

2. Process of Consent

We will explain to participants that the purpose of the study is to understand barriers pertaining to why blacks do not participate in clinical trials, assess their willingness to enroll in clinical trials, and ascertain whether or not they will refer others to participate in such trials. We will obtain participants consent to audio-record the debriefing session. The screening team will comprise ethnically concordant investigator: [name]. All participants will be reminded that their responses are confidential and that they may refuse to participate in the project or withdraw at any time without explanation, and further, that such action will in no way affect their future interactions with their health care provider, or with New York University Medical Center. To ensure confidentiality, data will be associated with an individual participant only by an assigned identification number, the code for which will be kept in a locked drawer that only the study investigators will have access to.

3. Number of subjects.

The proposed study expects to recruit a total of 100 participants from all recruitment strategies over a period of 9 months.

4. Gender of Subjects.

The study will include black men and women

5. Age of Subjects.

The sample frame will include black men and women 18 years old and older.

6. Racial and Ethnic Origin.

Our emphasis on blacks is justified by the low participation in clinical trials in this group.

7. Inclusion Criteria.

Self-reported race/ethnicity as African American, African, Caribbean American or black men and women; ages ≥ 18 years; accessible by telephone; no plans to move away from the region within the year following enrollment; consent to participate.

8. Exclusion Criteria.

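### Section V carries a 20-point gap over from a pilot on another behaviour without justifying it for tailored versus standard website, and 50 per arm gives that gap about 56% power, not the stated 80%

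*Combined protocol and SAP*

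**What the plan says.** Section V (Statistical Plan, Power Calculations) takes its rates from an earlier pilot by the same team, in which 45% of minority patients "adopted recommendations for medical treatments after exposure to tailored health messages, which compares to 25% who did without such exposure". It assumes a 20% increase in adopting health messages and says a sample of 100 gives adequate power for a preliminary test that "exposure to health messages will foster greater uptake of tailored health messages" and improve clinical trial health literacy. On size it states: "comparing 25% to 45% requires 50 participants per arm", for a two-tailed test at 80% power and alpha 0.05. It adds that a 20% gain would matter for public health, and ends by claiming power for participation rates between the arms, allowing for 23% attrition.

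The comparison actually made is described elsewhere. Under Control Condition (Section II): "Participants randomized to the control condition will have free access to the NYU standard clinical trials website". The same paragraph says: "Currently, there is no specific comparative effectiveness data evidencing superiority of any website or other format for increasing clinical trials literacy". Section III gives controls a pre-loaded tablet with verbal and paper instructions, restricts the tailored site by password to the exposure arm, and asks about ResearchMatch registration at 1 month. Section IV compares the arms on registering and on referring others.

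**The concern.** A power statement is only as good as the match between its planning rates and the trial's own contrast and outcome. Here both differ from the source, and the text does not bridge the gap. If being handed trial information of any kind moves people to act, some of that effect will appear in both arms and the difference between websites may be smaller than the pilot's. Registration may also have a quite different base rate from adopting treatment advice.

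What is at stake is how the result is read. A non-significant difference set against a claim of adequate power invites the conclusion that tailoring does not work, when the trial may only have been too small to tell.

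**Working it through.** **1. Source against use**

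| | Pilot behind 25%/45% | This trial |
|---|---|---|
| Behaviour | Adopting medical treatment recommendations | Registration, referral, willingness, literacy |
| Comparison group | Without tailored messages (what they did receive is not stated) | NYU standard clinical trials website, on a tablet, with instructions |
| Expected rates | 25% and 45% | None given for either website |

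Nothing in the documents links the two columns. The Control Condition paragraph cites research on patients' difficulty with generic materials, which supports a direction but gives no rate.

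**2. The hypothesis named as powered**

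Section III admits only the exposure arm to the tailored site, and Section II gives controls access at study completion. Uptake of tailored messages therefore has no control-arm value to compare with during the trial. The other half of the same sentence, clinical trial health literacy, can be compared: Table 1 lists Clinical Trials Literacy at all three visits with no restriction by arm.

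**3. The plan's own figure**

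Inputs from Section V: p1 = 0.25, p2 = 0.45, two-sided alpha 0.05, power 80%, stated answer 50 per arm. The mean rate is 0.35.

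n = [1.960·√(2·0.35·0.65) + 0.842·√(0.25·0.75 + 0.45·0.55)]² / 0.20²
= [1.960·√0.455 + 0.842·√0.435]² / 0.04
= (1.322 + 0.555)² / 0.04 = 88.1, so **89 per arm**.

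Other two-sided versions give 86 (unpooled), 88 (arcsine) and 98 (continuity-corrected). One-sided versions give 68 to 79. None gives 50. Allowing for 23% attrition, 89/0.77 = 115.6, so 116 per arm.

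**4. Power for 25% versus 45%**

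- 50 per arm: null SE = √(0.455/50) = 0.0954; alternative SE = √(0.435/50) = 0.0933. z = (0.20 − 1.960·0.0954)/0.0933 = 0.140, so power is **56%**. With a two-sided Fisher's exact test, the test Section V names for its literacy comparison, it is 48%.
- After attrition: 100·0.77 = 77, about 38 per arm. The SEs are 0.1094 and 0.1070, z = −0.135, power about **45%**.

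**5. What the fixed sample delivers**

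The control rates below are assumptions, since the documents give none for registration.

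| Assumed control rate | Difference with 80% power, 50 per arm | 38 per arm |
|---|---|---|
| 5% | about 20 points | about 24 |
| 10% | about 23 points | about 27 |
| 25% | about 27 points | about 31 |

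From a 25% control rate with 50 per arm, power for 10, 15 and 20 points is 19%, 36% and 56%.

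The 95% confidence interval half-width at 25%/45% is 1.96·0.0933 = 18.3 points with 50 per arm, and 1.96·0.1070 = 21.0 points with 38.

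**The case against.** The strongest reply is that the planning figure has a source and a rationale. It comes from the team's own pilot of tailored messages in minority patients, and Section V separately defends 20 points as important for public health. A worthwhile difference is a recognised basis for planning. The study is called a pilot and the test preliminary. All of this stands, and it rules out some stronger readings.

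- A reader might infer that the pilot's comparison group received no messages at all. The text says only that they lacked tailored messages; generic ones are not excluded. How much of the 20 points would survive against a standard website is therefore unknown.
- A reader might infer that the 20 points has no basis. The basis is indirect and its transfer unexplained, which is a lesser fault.
- A reader might infer that real power must be very low. If the standard site lifted controls to 30% or 35% against 45%, power at 50 per arm would be 34% or 17%. But those rates are assumed. If registration were rarer and the 20 points held, 5% versus 25% would have 81% power and 10% versus 30% would have 71%.
- A reader might take registration as the trial's only outcome. Willingness, behavioural intent, referral and literacy are named too, and no single primary endpoint is tied to these rates.

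The reply does not supply the missing justification, and it does not touch the arithmetic. Nor does the other power statement in Section V, an effect size of 0.32. Read as a standardised mean difference, it gives about 36% power at 50 per arm. Read as Cohen's w it gives about 89% at N = 100, but 25% versus 45% corresponds to w = 0.20/(2·√(0.35·0.65)) = 0.21, a smaller effect.

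**Conclusion.** The point holds in a limited form. The 25% and 45% describe another behaviour, compared with and without tailored messages, and the protocol does not justify carrying the gap over to tailored versus standard website on registration or participation. Its own text says no comparative data favour any website for clinical trials literacy. Uptake of tailored messages is not a between-arm outcome. Separately, the stated 80% power is wrong on the plan's own inputs: about 56% with 50 per arm and about 45% after attrition.

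The last two figures need only Section V's rates, alpha, sample size and attrition, with attrition equal in the arms. The detectable differences depend also on assumed control rates. The documents do not show what the true difference between the websites is, so the effect of the borrowed gap on real power cannot be sized, only bracketed.

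**What to change.** Reword Section V:

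1. State that 25%/45% is an indirect pilot contrast for another behaviour, and that 20 points is a worthwhile target rather than the expected difference between websites.
2. Replace uptake of tailored messages as the powered hypothesis with a between-arm outcome measured in both arms, such as registration, which Section V already names.
3. Replace the 80% claim with the detectable differences in the table above, for 50 and 38 per arm, and with power of about 19%, 36% and 56% for 10, 15 and 20 points from a 25% control rate. Label every control rate as an assumption.
4. Commit to reporting the arm difference with a 95% confidence interval, noting a half-width of about 18 to 21 points if rates fall near 25% and 45%. Keep the existing description of the test as preliminary.

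The cost is rewording only, with no change in enrolment. The downside is that the stated power becomes less favourable.
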